#### **Analysis Visit Window:**

By visit summaries will be based on the nominal/scheduled visit as reported in eCRF and will be grouped by Day 1, 2, 3, 4, 5, 6, 7, 10, 14, 28 and 60.

For (telephone contact) TC follow up visits and unscheduled Discharge visits, analysis visit windows will be applied as in [Table 2](#) and [Table 3](#) below. Note, analysis visit windows are only used for by visit summaries, not for time to event calculation which will be based on actual date of data collected. TC follow up visits and Discharge visits that are not in any of the analysis visit windows, will be excluded from summaries and only presented in listings.

**Table 2 Analysis Visit Window for TC follow up visits**

mapped to	Visit Window
Day 7	Day 7 ± 2 days
Day 14	Day 14 ± 2 days
Day 28	Day 28 ± 5 days
Day 60	Day 60 ± 5 days

**Table 3 Analysis Visit Window for unscheduled Discharge visits**

mapped to	Visit Window
Day 7	Day 8
Day 10	Day 10 ± 1 days
Day 14	Day 14 ± 2 days
Day 28	Day 28 ± 5 days
Day 60	Day 60 ± 5 days

In case several outcomes are available for the nominal/scheduled analysis visits, the latest non-missing result will be used for summaries.

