A single dose of study drug will be administered on Day 1. All study drug will be administered in the hospital setting; patients who are intubated after randomization but prior to study drug administration are no longer eligible to receive study drug. As this is a single-dose study, the treatment period is 1 day. Thereafter, all patients will be followed for 60 days post-treatment. The schedule of study assessments over this period is dependent on the duration of hospitalization and whether or not the patient requires intubation (ie, non-intubated and intubated patients).

- **While hospitalized**, non-intubated patients will have study assessments performed while hospitalized on Days 2, 3, 4, 5, 6, 7, 10, and Day 14 and/or Discharge.
 - If the non-intubated patient is discharged prior to Day 14, the assessments scheduled for Day 14 and/or Discharge will be completed at the time of discharge. If discharge occurs on another scheduled study assessment day (ie, any day between Day 2 and 10), the Day 14 and/or Discharge assessments

supersede that study assessment day and the patient then will proceed to outpatient telephone contact (TC) follow-up visits.

- If the patient is discharged prior to Day 14, then outpatient TC follow-up visits are to be conducted on Day 7 (as applicable) and Day 14.
- If the non-intubated patient is discharged after Day 14, the patient is to have the assessments scheduled for Day 14 and/or Discharge performed on the day of discharge. If the patient is hospitalized for ≥ 21 days, the Day 14 assessments are to be performed weekly (Days 21, 28, 35, etc.) until discharge (with the exception of PK, which is to be done only at Day 28). After discharge, the patient will proceed to the next scheduled outpatient TC follow-up visit. (Thus, if a patient remains hospitalized on Day 28, the Day 28 TC follow-up visit need not be conducted.)
- ***In the event a patient is intubated***, SOC assessments and interventions will supersede study assessments while intubated and for the duration of intubation¹, with clinical assessments collected as available per the institution's electronic medical records.
 - Patients will resume the study assessment schedule upon extubation. (Thus, for example, if an intubated patient is extubated on Day 7, they will resume the study assessment schedule on Day 7).

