### 3.1.1 Hospitalized, Non-intubated Patients

**While hospitalized**, non-intubated patients will have study assessments performed on Days 2, 3, 4, 5, 6, 7, 10, and 14 and/or Discharge.

If the non-intubated patient is discharged prior to Day 14, the assessments scheduled for Day 14 and/or discharge will be completed at the time of discharge. If discharge occurs on another scheduled study assessment day (ie, any day between Days 2 and 10), the Day 14 and/or discharge assessments supersede that study assessment day and the patient then will proceed to outpatient telephone contact (TC) follow-up visits. If a patient is discharged prior to Day 14, then outpatient TC follow-up visits are to be conducted on Day 7 (as applicable) and Day 14.

If the non-intubated patient is discharged on Days 15-20, the patient is to have the assessments scheduled for Day 14 and/or discharge performed on the day of discharge. If the patient is hospitalized for  $\geq 21$  days, the Day 14 assessments are to be performed weekly (Days 21, 28, 35, etc.) until discharge (with the exception of pharmacokinetics [PK], which is to be done only at Day 28). After discharge, the patient will proceed to the next scheduled outpatient TC follow-up visit. (Thus, if a patient remains hospitalized on Day 28, the Day 28 TC follow-up visit need not be conducted.)

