Days with fever up to Day 14 will be used as a sensitivity analysis. Days will be calculated the same as described for Days of supplemental oxygen (O2) up to Day 14.

Change from baseline in WHO Ordinal Scale score

The description of the WHO Ordinal Scale score is shown in [Section 6.2](#). The Number and percentage of patients on WHO Scale scores and change from baseline (-7, -6, -5, -4, -3, -1, 0, 1, 2, 3, 4) will be presented by visit. Shift table will be presented by visit as well.

Simple Ordinal logistic regression on the WHO Scale score at each visit (Days 5, 7, 14, 28, and 60) will be performed to compare ATYR1923 1 mg/kg versus Placebo and ATYR1923 3 mg/kg versus Placebo. Firth logistic regression ([Firth, 1993](#)) on the collapsed WHO Ordinal Scale (0-3 versus 4-8) at each visit (Days 5, 7, 14, 28, and 60) will be performed as well.

Distribution of WHO Ordinal Scale at 1, 2, 3, 4, 5, 6, 7, 10, 14, 28 and 60 days will be visualized by treatment group using an stacked bar chart. These figures will only consider scheduled assessments and in case the scheduled assessment is not available the mapped unscheduled TC follow up assessments as defined in [Section 4.2](#).

Time to Improvement in Clinical Status

Time to improvement in days is the time in which the patient sees a decrease after study treatment in the WHO Ordinal Scale score from baseline by at least 1 point, derived as:

date of decrease in WHO scale compared to baseline by at least 1 point - study drug administration date; or date of discharge from hospital - study drug administration date, whichever occurs first.

In the case that a patient has not decreased in the WHO scale or withdraws from the study, they will be censored at EOS date. Time to improvement will be analyzed using the Kaplan-Meier methods and Cox Proportional Hazards model as described in the above.

Repeat analysis above for improvement of WHO Ordinal Scale score by at least 2 points.

Additionally, time to improvement will be analyzed using an adapted derivation: date of decrease in WHO scale compared to baseline by at least 1 point - randomization date; or date of discharge from hospital - randomization date, whichever occurs first.

Related output will be noted as sensitivity analysis.

Time to improvement (by at least 1 and 2 points) will be analyzed based on mITT and EE Set. Sensitivity analysis for time to improvement will be analyzed based on mITT only.

*All-cause mortality*

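### SAP 4.2 lets a discharge score taken after the target day replace an available on-time WHO score, so by-visit WHO results lean slightly towards improvement in every arm and can disagree with the SAP's own bar chart

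*SAP*

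**What the plan says.** SAP 4.2 bases by-visit summaries on the nominal visit and adds one exception: "For (telephone contact) TC follow up visits and unscheduled Discharge visits, analysis visit windows will be applied". Table 3, headed "Analysis Visit Window for unscheduled Discharge visits", sends Day 8 to Day 7, Days 9-11 to Day 10, Days 12-16 to Day 14, Days 23-33 to Day 28 and Days 55-65 to Day 60. The rule for choosing among several results at one visit follows: "the latest non-missing result will be used for summaries". It gives no priority to the assessment made on the scheduled day.

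The assessment schedule can give one patient both scores. SAP 3.1.1 states: "If the non-intubated patient is discharged on Days 15-20, the patient is to have the assessments scheduled for Day 14" or discharge done again on the day of leaving. For stays of 21 days or more, "the Day 14 assessments are to be performed weekly (Days 21, 28, 35, etc.) until discharge", which supplies an inpatient Day 28 score. The protocol synopsis is wider on later discharges: "If the non-intubated patient is discharged after Day 14, the patient is to have the assessments scheduled for Day 14 and/or Discharge performed" on the discharge day.

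For the stacked bar chart of the same scores, SAP 4.9.4.1 (Change from baseline in WHO Ordinal Scale score) sets the opposite priority: "These figures will only consider scheduled assessments and in case the scheduled assessment is not available the mapped unscheduled TC follow up assessments". Mapped discharge visits are not named there. The same subsection lists the change categories as -7 to -3, then -1 to 4, so -2 and +5 are absent.

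**The concern.** A patient discharged one or two days after Day 14 was in hospital on Day 14 and was due a score that day. The rule discards that score in favour of one taken later, at a moment chosen because the patient was fit to leave. A patient who is intubated or dies in hospital on Day 15 has no such window, so the Day 14 score stands. The selection is therefore one-sided for inpatients. It affects the by-visit WHO tables and shift tables and, if they use the same values, the ordinal and Firth logistic regressions at Days 7, 14 and 28.

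There is also a consistency problem. One secondary endpoint would be shown in tables under one selection rule and in a figure under another, so the counts need not match. As listed, the change table also has no row for a two-point improvement, although the SAP analyses time to improvement by at least 2 points.

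**Working it through.** The documents give no planned figure to reproduce: there is no power calculation and no assumed discharge rate. The check has four steps.

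**1. Which discharge days can overwrite.** From Table 3, take the window days that fall after the nominal day; k is their number.

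| Target day | Window | Overwriting days | k |
|---|---|---|---|
| 7 | 8 | 8 | 1 |
| 10 | 9-11 | 11 | 1 |
| 14 | 12-16 | 15, 16 | 2 |
| 28 | 23-33 | 29-33 | 5 |

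The Day 7 row is the plainest case. Its only window day is Day 8, and anyone discharged then was an inpatient on Day 7. That row can only fill a missed Day 7 score or replace an on-time one. Day 60 has the same form (Days 61-65), but follow-up ends at Day 60 and the share below would be 1.1% or less.

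**2. How many patients.** Assume a constant daily discharge probability h from Day 2 onwards. This is an assumption, shown over 5% to 16%. The share in hospital on day d is S(d) = (1-h)^(d-1).

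- Share of those still inpatient who are overwritten: 1-(1-h)^k.
- Share of all patients: S(d) - S(d+k).

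Example, Day 14 with h = 10%: S(14) = 0.9^13 = 25.4%; 1-0.9^2 = 19.0%; product 4.8%.

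| Target day | Of inpatients: h = 5 / 10 / 15 / 16% | Of all patients: h = 5 / 10 / 15 / 16% |
|---|---|---|
| 7 | 5.0 / 10.0 / 15.0 / 16.0% | 3.7 / 5.3 / 5.7 / 5.6% |
| 10 | 5.0 / 10.0 / 15.0 / 16.0% | 3.2 / 3.9 / 3.5 / 3.3% |
| 14 | 9.8 / 19.0 / 27.8 / 29.4% | 5.0 / 4.8 / 3.4 / 3.1% |
| 28 | 22.6 / 41.0 / 55.6 / 58.2% | 5.7 / 2.4 / 0.7 / 0.5% |

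The largest share of all patients in this range is 5.7%. With 30 patients randomized 1:1:1, that is 10 x 0.057 = about 0.6 patients per arm at one visit. It is an upper bound on the shift in the proportion scoring 3 or less, because it counts every overwrite as a move from 4 or more to 3 or less. One actual patient moves an arm by 1/10 = 10 points.

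**3. Between-arm difference.** Take the difference in the proportion discharged by d and by d+k. With equal h it is 0 both times. With unequal h (assumed pairs), in percentage points:

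| h, slower v faster arm | Day 7 | Day 14 | Day 28 |
|---|---|---|---|
| 8% v 12% | 14.2 to 14.9 | 14.8 to 13.9 | 7.4 to 5.3 |
| 5% v 10% | 20.4 to 22.0 | 25.9 to 25.7 | 19.2 to 15.9 |
| 10% v 15% | 15.4 to 15.8 | 13.3 to 11.9 | 4.6 to 2.9 |

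The difference rises slightly at Day 7 and falls at Days 14 and 28.

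**4. Tables against figure, and the change list.** Take a hypothetical patient with baseline 4, a Day 14 score of 4, and a score of 2 at discharge on Day 15. The table uses 2 and the bar chart uses 4. The change in the table is -2, which has no category. Intubated patients are excluded, so baseline should not exceed 5, and -6 and -7 cannot occur. A patient can qualify on respiratory rate alone without oxygen, so a baseline of 3 is possible and death would then be +5. The attainable range is -5 to +5.

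**The case against.** Several limits on this point stand.

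A reader might infer that every overwrite records an improvement. The documents do not support that. SAP 4.9.4.1 says that some patients left hospital still on oxygen, and it has derivation steps for a score of 4 or more on the day of discharge. Scores are taken between 06:00 and 10:00 or per local practice, so a discharge-day score may still be an inpatient score. A patient close to discharge may already score 3, and the collapsed 0-3 versus 4-8 outcome then does not move.

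A reader might also take the 41-58% at Day 28 (h of 10% or more) as the share of data affected. It applies only to those still in hospital. Under the same assumptions these are 5.8% of patients or fewer, so 0.5-2.4% of all patients are overwritten.

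The reach also has limits. SAP 4.2 applies the windows to by-visit summaries; that the regressions use the windowed values is the natural reading of an analysis at each visit, but it is not stated. SAP 3.1.1 names the discharge-day assessment only for Days 15-20, so for non-intubated patients the Day 29-33 route rests on the protocol synopsis. Where a patient leaves before the target day and then has an on-time telephone visit, the latest result is the on-time one, so the fault is confined to discharges after the target day. The telephone windows can bring in late scores in either direction, but only after discharge.

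The missing -2 looks like a slip in a consecutive list. Two-point improvements would still be visible in the shift tables and in the time-to-improvement analysis.

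None of this explains why a later score should displace one taken on the scheduled day, or why the figure should follow a different rule.

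**Conclusion.** The point holds as a minor one. For discharges shortly after Days 7, 10, 14 and 28, the selection rule replaces on-time WHO scores with later discharge scores, with no counterpart for in-hospital worsening. By-visit scores therefore lean towards improvement in every arm, by at most about 6 percentage points of patients scoring 3 or less at any one visit. That bound rests on the assumed constant discharge probability of 5-16% per day. Tables and bar chart can disagree for the same patients.

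A reader might conclude that the rule favours ATYR1923. The documents do not show this. The rule applies to all arms alike, equal discharge rates leave the expected difference at zero, and unequal rates shift it slightly in either direction. Nor does the SAP revision history list the visit windows among the changes made after unblinding. Time-to-event endpoints use actual dates and are unaffected. The primary endpoint is treatment-emergent adverse events, and efficacy p-values are declared exploratory.

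**What to change.** In SAP 4.2, for WHO scores only, use the assessment made on the scheduled day when it exists. Only if it is missing, use the mapped discharge or telephone assessment closest to the target day, with a stated tie rule (for example, discharge on Day 12 and telephone visit on Day 16 are equally far from Day 14: take the later). Apply this to the by-visit tables, the shift tables, the ordinal and Firth regressions and the bar chart, and say that the regressions use these values. State that mapped discharge visits may also fill gaps in the figure. Limit the change to WHO scores, because the laboratory and biomarker sections set their own selection rules. In SAP 4.9.4.1, list change categories from -5 to +5, including -2 and +5.

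With this rule, no on-time score is overwritten at any visit. The cost is a few lines of SAP text and minor programming. The small downside is timing: SAP versions 2.0 and 3.0 already contain changes made after unblinding, so this one should be labelled post hoc in line with SAP 3.2, with the current latest-result rule kept as a sensitivity display.

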## **Treatment Descriptors**

Displayed columns will be labelled and ordered:

- Placebo,
- ATYR1923 1 mg/kg,
- ATYR1923 3 mg/kg,
- ATYR1923 Total,
- All Patients.

## **4.3 Missing Data**

### **4.3.1 Imputation of Non-Date Missing Data**

Missing data occurs when any requested data is not provided, leading to blank fields on the collection instrument. These data will be indicated by the use of a “blank” in subject listing displays. Answers such as “Not applicable” and “Not evaluable” are not considered to be missing data and should be displayed as such.

Subjects with the designation of treatment relationship for AEs and SAEs missing will have the worst realistic case assumed to impute the relationship: if relationship is missing and the AE started on or after study drug administration it will be assumed to be “related” (worst case). If the AE with missing relationship started before study drug administration (eg, during Screening Period), it will be considered as “not related” (realistic case). Missing Severity will be assumed to be “Life-threatening” (worst case). In listings these imputed relationships and causalities will be flagged.

For variables which determine the proportion of events, all subjects in the respective analysis set will be included in the denominator when calculating the percentages irrespective of whether their outcome may be missing.

Handling of complete or partial missing dates for Adverse Events or reported Concomitant Medication will be given in the following Section.

All other missing data will not be imputed.

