8.6.3. Adverse Events

AEs will be recorded from the time of initiation of study drug administration through the last visit for a patient. Any clinically significant observations in results of clinical laboratory, 12-lead electrocardiograms (ECGs) (if performed per SOC), vital signs, pulse oximetry, or physical examinations are to be recorded as part of the patient's medical history if occurring prior to start of dosing and as an AE if occurring after the start of study drug administration at Day 1, where the finding represents a change from Baseline.

A TEAE is defined as any event not present prior to (the first) administration of the study drug or any event already present that worsens in either intensity or frequency following exposure to the study drug.

An AE which occurs prior to (the first) administration of the study drug will be considered a pre-treatment AE.

AEs that occur during or within 24 hours after study drug injection should be captured as individual signs and symptoms (eg, dyspnea, rash, flushing) rather than a diagnosis of allergic reaction or IRR.

Patients will be asked non-leading questions and evaluated to determine the occurrence of AEs. All AEs reported or observed spontaneously during the course of the study will be recorded.

The intensity of each AE will be rated by the Investigator using the National Cancer Institute Common Terminology Criteria for Adverse Events (NCI CTCAE), version 5.0 (available at: https://ctep.cancer.gov/protocolDevelopment/electronic_applications/docs/CTCAE_v5_Quick_Reference_8.5x11.pdf).

AEs not listed on the NCI CTCAE V5.0 are to be rated by the Investigator as "mild (Grade 1)", "moderate (Grade 2)", "severe" (Grade 3), "life-threatening"(Grade 4), or "fatal" (Grade 5).

The relationship between the AEs and the study drug will be indicated as "not related", "unlikely related", "possibly related", or "related". AEs assessed as "possibly related" or "related" will be considered to be related to the study drug whereas AEs assessed as "not related" or "unlikely related" will be considered not to be related to the study drug.

Details on the rating of the severity of the AEs and relationship to the study treatment are given in [Section 9.2](#).

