9.1.3. Serious Adverse Event

An AE or suspected adverse reaction is considered “serious” if, in the view of either the Investigator or Sponsor, it results in any of the following outcomes:

- is fatal.
For the purposes of this study, death due to SARS-CoV2 infection is not considered an SAE.
- is life-threatening (ie, places the patient at immediate risk of death).

- requires in-patient hospitalization (overnight stay) or prolongation of existing hospitalization.

As all patients are required to be hospitalized as inpatients to be eligible for this study, any event other than SARS-CoV2 infection requiring prolonging of inpatient hospitalization and/or rehospitalization after discharge will be considered an SAE. Hospitalization due to SARS-CoV2 infection is not considered an SAE, provided that it did not deteriorate in an unexpected manner during the study.

- results in persistent or significant disability/incapacity.
- is a congenital anomaly/birth defect.
- is an important medical event; an important medical event is an event that may not result in death, be life-threatening, or require hospitalization but may be considered an SAE when, based upon appropriate medical judgment, it may jeopardize the patient and may require medical or surgical intervention to prevent one of the outcomes listed in the definitions for SAEs. Examples of such medical events include allergic bronchospasm requiring intensive treatment in an emergency room or at home, blood dyscrasias or convulsions that do not result in inpatient hospitalization, or the development of drug dependency or drug abuse.

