9.2.4. Intensity

The intensity of each AE is to be assessed by the Investigator using the NCI CTCAE, version 5.0 (available at:

https://ctep.cancer.gov/protocolDevelopment/electronic_applications/docs/CTCAE_v5_Quick_Reference_8.5x11.pdf).

AEs not listed on the NCI CTCAE V5.0 are to be rated by the Investigator according to the categories in [Table 3](#).

Table 3: Criteria for Determination of Adverse Event Intensity

Intensity	Definition
Mild (Grade 1):	Asymptomatic or mild symptoms: clinical or diagnostic observations only; intervention not indicated.
Moderate (Grade 2)	Minimal, local, or non-invasive intervention indicated; limiting age-appropriate instrumental activities of daily living.
Severe (Grade 3):	Severe or medically significant but not immediately life threatening: hospitalization or prolongation of hospitalization indicated; disabling; limiting self-care activities of daily living; incapacitating with inability to work or perform normal daily activity.
Life-threatening (Grade 4):	Consequences: urgent intervention indicated.
Fatal (Grade 5)	AE resulted in death

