### 3.4 Endpoints

#### 3.4.1 Primary

- Incidence of TEAEs, including serious and severe TEAEs, overall and by severity.

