### 4.10.2 Adverse Events

Adverse events will be coded using the MedDRA Version 23.0 or higher.

Treatment-emergent AEs (TEAE) are defined as AEs that either start or worsen in severity on or after the date/time of study drug administration and through the end of study. Partial date imputation was specified in [Section 4.3](#). Imputed dates will only be used for TEAE definition.

An overall summary table of TEAEs will be provided with the number and percentage of patients (incidence) reporting an event along with the total number of events presented for the following categories:

- All TEAEs,
- TEAEs related to Study Drug,
- TEAEs by severity,
- Severity grade 3 and higher TEAEs,
- Severity grade 3 and higher TEAEs related to Study Drug,

- Serious TEAEs,
- Study drug-related serious AEs (SAEs),
- Fatal TEAEs,
- TEAEs leading to study discontinuation,
- SAEs related to COVID-19,
- TEAEs suspected as infusion-related reactions.

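### SAP 4.3.1 treats Grade 4 as the worst case for a missing AE severity although the scale ends at Grade 5, so a fatal event with a blank grade would be tabulated as Grade 4; imputed severity is also not named in the listing flag

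*SAP*

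**What the plan says.** The severity rule in SAP 4.3.1 is one unconditional sentence: "Missing Severity will be assumed to be “Life-threatening” (worst case". It does not look at the event's outcome, its seriousness, or whether it began before dosing. The relationship rule in the same section does separate events by onset: for one that began before dosing, "it will be considered as “not related” (realistic case". The section then says: "In listings these imputed relationships and causalities will be flagged".

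SAP 4.10.2.1 refers back to this rule for missing severity in the AE summaries. Those summaries support the primary endpoint in SAP 3.4.1: "Incidence of TEAEs, including serious and severe TEAEs, overall and by severity".

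The protocol's severity scale has five grades. Section 8.6.3 ends its list with "or 'fatal' (Grade 5", and Table 3 in Section 9.2.4 defines that grade as "AE resulted in death". Death is also held in a separate AE outcome field (Protocol 9.2.5, Table 4), which is reserved for the single event judged to be the primary cause of death. Among the criteria for a serious event in Protocol 9.1.3 is that it "is life-threatening (ie, places the patient at immediate risk of death".

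**The concern.** An imputation rule that is called worst case should not produce a milder value than the record supports. Here a death documented in the outcome field can be shown one grade below fatal, in a table that belongs to the primary endpoint. In the other direction, an event that the investigator marked non-serious can be shown as life-threatening, so the severity and seriousness tables would describe the same event differently. If relationship is also blank on a post-dose event, SAP 4.3.1 makes it related, and one incomplete record then enters the table of drug-related events of Grade 3 or higher.

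With about 10 patients per arm, a reader will notice a single patient in these rows. An imputed high grade in placebo flatters the drug; in a dose arm it suggests a safety signal. If imputed grades are not flagged, the reader cannot tell either from an observed event.

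**Working it through.** The plan states no figure to reproduce: it gives no power, no expected event rate and no expected rate of missing grades. The check is a trace of the rule, followed by the size of one record.

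**1. Trace of the rule for a blank grade**

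| Recorded information | Grade under SAP 4.3.1 | Consequence |
|---|---|---|
| Outcome fatal | 4 | Should be 5 on the protocol scale; the Grade 3 or higher count is unchanged |
| Marked non-serious, started after dosing | 4 | Grade 4 in the severity table, absent from the serious TEAE table |
| Relationship also blank, started after dosing | 4 and related | Enters the drug-related Grade 3 or higher table |

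For the fatal case, SAP 4.10.2 lists fatal TEAEs as a separate row but does not say whether it is derived from outcome or from grade. If from outcome, that row counts a death that the Grade 5 row omits. If from grade, the death is missing from both.

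**2. Size of one record**

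Inputs: 30 patients randomized 1:1:1 (SAP 3.1.4), so 30/3 = 10 per arm and 2 × 10 = 20 in ATYR1923 Total.

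- Grade 3 or higher row, patient with no other TEAE of Grade 3 or higher: 1/10 = 10 percentage points in an arm and 1/20 = 5 points in ATYR1923 Total.
- The same row, patient who already has a TEAE of Grade 3 or higher: 0 points.
- Fatal event with a blank grade: the patient moves from the Grade 5 to the Grade 4 row of the maximum-severity table (10 points in an arm, 5 in Total). Only one event per patient carries the fatal outcome, so no other event restores the Grade 5.

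**3. Chance that the rule is used at all**

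Let q be the share of patients with at least one blank-grade TEAE. The documents do not give q, so the values below are assumptions. Taking patients as independent, P(at least one) = 1 − (1 − q)^n. For example, with q = 2% and n = 30, 1 − 0.98^30 = 45.5%.

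| q (assumed) | arm of 10 | Total of 20 | all 30 |
|---|---|---|---|
| 1% | 9.6% | 18.2% | 26.0% |
| 2% | 18.3% | 33.2% | 45.5% |
| 5% | 40.1% | 64.2% | 78.5% |
| 10% | 65.1% | 87.8% | 95.8% |

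These are chances that a blank-grade TEAE exists, not that a row moves. With q = 0 nothing changes.

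**4. Could the rule affect which events count as TEAEs?**

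SAP 4.10.2 counts events that "either start or worsen in severity on or after the date/time of study drug administration". Suppose, which the SAP does not state, that imputed severity were used in that comparison. There are 10 possible upward shifts between grades 1 and 5.

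- Earlier grade blank and set to 4: the 4 shifts that end at Grade 5 are still seen; the 6 that end at Grades 2 to 4 are lost.
- Later grade blank and set to 4: any earlier Grade 1, 2 or 3 appears to have worsened, whether it did or not.

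The error could go either way, and it arises only under that supposition.

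**The case against.** The case for leaving the rule alone has several parts.

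- **Blank grades should be rare.** Protocol 9.3 requires intensity in every AE report, Section 12.2 asks for an explanation of missing data, and entries are verified against source. This stands, and it is why the effect is conditional.
- **Deaths are visible elsewhere.** They have an outcome category, a fatal TEAE row, table and listing, and a separate mortality summary. This limits the harm, but it does not make the by-severity table right, and the source of the fatal TEAE row is unstated.
- **Seriousness and intensity are separate assessments.** Table 3 describes Grade 4 by the need for urgent intervention; the seriousness criterion refers to immediate risk of death. So a non-serious Grade 4 is a tension between tables, not a strict contradiction. This stands.
- **The flag sentence may simply be loose drafting.** It follows directly after the severity rule, and the intent may have been to include severity. That is plausible, but SAP 4.10.2.1 uses causality to mean relatedness, so severity is not named as written.
- **The analysis is descriptive.** The study is exploratory and no test of the primary endpoint is specified. This stands.

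A reader might also infer that the rule hides worsening of pre-dose events. The documents do not establish this. AEs are recorded from the start of dosing and clinically significant pre-dose findings go to medical history (Protocol 8.6.3). Only SAEs are collected from consent (Protocol 9.4), so few pre-dose records would be expected. The SAP mentions imputed dates, not imputed severity, for the TEAE definition, and the opposite error is just as possible.

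A reader might further conclude that Grade 3 is a better default, or that pre-dose blanks should be Grade 1. Neither follows. Grade 3 leaves the Grade 3 or higher count exactly as it is under Grade 4. It also sits no more easily with a non-serious record, because Table 3 ties Grade 3 to prolonged hospitalization, itself a seriousness criterion. Grade 1 would label pre-dose SAEs as mild and turn any later, higher grade into an artificial TEAE.

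**Conclusion.** The concern holds in a limited form. Followed as written, SAP 4.3.1 assigns Grade 4 to a fatal event whose grade is blank, so the label of worst case is wrong and the severity table can disagree with the outcome field. The tension with non-serious records and the incomplete flag sentence are smaller points. Whether imputed severity may enter the worsening test is an unanswered question, not a demonstrated error.

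The shift of 10 points per arm, or 5 in ATYR1923 Total, assumes full enrolment at 10 per arm with all patients dosed. For the Grade 3 or higher row it also assumes an affected patient with no other such TEAE. The number of blank grades is unknown; if there are none, no result changes. Because the rule acts on the primary endpoint, it is worth correcting, but it does not threaten a formal inference.

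**What to change.** In SAP 4.3.1:

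1. When severity is missing and the AE outcome is fatal, set Grade 5; otherwise keep Grade 4. Use the outcome field, not seriousness, because Protocol 9.1.3 does not count death from SARS-CoV-2 infection as an SAE.
2. State that imputed severity is not used to judge worsening for TEAE status.
3. Name severity in the sentence on flagging imputed values in listings.
4. Show the by-severity and Grade 3 or higher rows with and without imputed grades, and give the number of imputed grades by arm.

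The revision history shows that SAP versions 2.0 and 3.0 already contain post-unblinding modifications, so this change should be documented as post-unblinding too. Showing both sets of rows guards against the appearance of choosing a rule after seeing the data.

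The cost is a slightly longer rule, a few lines of programming and some repeated rows. No new data are needed.
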